6.4.2.2 Toxicity management

Methods to improve patient's symptoms such as use of anticholinergics or antibiotics is allowed at the treating physician's discretion as per usual standard of care. Recommendations for management of Intravesical BCG-specific toxicities are shown in **Table 6**.

Table 6 Intravesical BCG related symptom alleviation and toxicity management

Toxicity	Recommendations
Transient symptoms: urinary frequency, urgency, dysuria, cystitis, malaise, fever < 38.5°C	Expected after intravesical BCG and usually resolves within 48 hrs. Consider symptomatic treatment (anticholinergics, pyridium, acetaminophen). Consider urine culture. Continue intravesical BCG treatment.
Persistent (> 48hr) fever < 38.5°C, cystitis, malaise	Urine culture; hold BCG until symptoms subside.
Fever > 38.5°C for 12-24 h	Urine culture; if culture is negative, consider Isoniazid 300 mg daily for 3 months; May resume intravesical BCG when asymptomatic.

Toxicity	Recommendations
Acute severe illness, local or systemic pneumonitis, hepatitis, prostatitis, ureteral obstruction, renal abscess, persisting high fever > 39°C	Isoniazid 300 mg, rifampin 600 mg and/or ethambutol 1200 mg, daily for 6 months; Discontinue intravesical BCG.
Sepsis	Isoniazid 300 mg, rifampin 600 mg and/or ethambutol 1200 mg daily for 6 months; cycloserine 500 mg twice daily orally; high-dose corticosteroids immediately; Discontinue intravesical BCG.

6.5 Supportive Care

All supportive measures consistent with optimal patient care will be given throughout the study.

6.6 Treatment Duration

Patients who complete BCG induction and the Month 3 maintenance treatment without unacceptable toxicity may continue a maintenance treatment regimen up to Month 12 as per study schema. Avelumab treatment will end at the conclusion of Month 12 maintenance BCG therapy. Additional BCG maintenance monotherapy will be at the discretion of the treating physician and considered standard of care.

6.7 Treatment Discontinuation

Patients must permanently discontinue study treatment (avelumab and BCG) if they experience any of the following:

- Intolerable toxicity related to study treatment, including development of an immune mediated adverse event determined by the investigator to be unacceptable given the individual patient's potential response to therapy and severity of the event
- Any medical condition that may jeopardize the patient's safety if he or she continues study treatment
- Investigator determines it is in the best interest of the patient
- Use of another non-protocol anti-cancer therapy
- Pregnancy
- Loss of clinical benefit as determined by the investigator after an integrated assessment of cystoscopy, radiographic and local biopsy results (if available), and clinical status (e.g., symptomatic deterioration such as pain secondary to disease)
- Patients have Cystoscopy or Radiographic disease progression or symptomatic deterioration attributed to disease progression

The primary reason for study treatment discontinuation should be documented in the patient's medical records. Patients who discontinue study treatment prematurely will be replaced.

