5.2.1 Definition of Dose limiting toxicity

During safety lead-in phase, Dose limiting toxicity (DLT) will be monitored during the first 6 weeks of the combination avelumab and intravesical BCG. DLTs will be defined as any and all adverse events at least possibly related to study drug which occur in the DLT evaluation period and meet the criteria below, as evaluated by the NCI-CTCAE version 5.0.

Note: DLTs and other toxicities will be discussed between the Principal Investigator, and the Data Safety Monitoring Committee (DSMC). The discussions are the basis for the decisions regarding dose expansion (or de-escalation) according to the rules of the protocol.

DLT will be classified as either hematologic or non-hematologic toxicity (assessed in accordance with the CTCAE Version 5.0 criteria).

The following are DLTs:

1. Toxicity causing greater than 2 weeks of dose delay. For example, if a subject has dose delay greater than 2 weeks due to an AE, such AE is a DLT.
2. Grade 4 neutropenia greater than 5 days.
3. ALT/AST $> 3x$ ULN with bilirubin $> 2x$ ULN without another explanation (e.g., cholestasis)
4. Any Grade 3 hypersensitivity reaction is a DLT
5. Grade 4 thrombocytopenia of any duration
6. Grade 3 thrombocytopenia with significant hemorrhage of any duration
7. Febrile neutropenia

And, any non-hematological Grade ≥ 3 toxicities will be a DLT.

The following may be considered as exceptions to DLTs:

1. Grade 3 nausea, vomiting, or diarrhea and Grade 4 vomiting or diarrhea in the absence of maximal medical therapy that resolves in 72 hours
2. Grade 3 fatigue lasting < 5 days
3. Grade 3 hypertension that can be controlled with medical therapy
4. An increase of indirect (unconjugated) bilirubin indicative of Gilbert's syndrome
5. Serum lipase and/or serum amylase CTCAE Grade 3 ≤ 7 consecutive days without clinical signs or symptoms of pancreatitis

5.2.1.1 Definition of DLT Evaluable Population:

Patients enrolled in safety lead-in cohort who receive at least 4 doses and complete the DLT observation period (the first 42 days of induction treatment), unless the patient discontinued the study treatment due to a DLT.

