8.2.1 Definition of Evaluable Patients for Efficacy Analysis

Evaluable patients will be defined as patients who receive at least 5 doses each of intravesical BCG and avelumab IV during induction treatment (first 8 weeks) and complete the first post-treatment cystoscopy and/or urine cytology for tumor assessment. Patients who discontinued study treatment due to toxicity incurred by previous therapy will be evaluated for safety analysis, but will be replaced by additional patients for the efficacy analysis.

Patients removed from study for early withdraw or hypersensitivity reactions will be replaced if they have received less than 5 doses of study treatment during induction treatment, but will be included in the safety analysis.

Patients who do not receive at least 5 doses of intravesical BCG and avelumab IV during induction treatment will be considered unevaluable for efficacy analysis and will be replaced unless the missed doses were due to development of grade 3-4 adverse events related to study treatment.

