10.3 Accrual and Study Duration

This is a single arm, phase Ib study. Total 18 evaluable patients will be enrolled in the Stephenson Cancer Center. More than 40 patients with bladder cancer will initiate intravesical BCG treatment in our Urologic Oncology clinic each year, including approximately 40% patients with BCG-treated but unresponsive NMIBC (persistent or recurrent) who are hopefully eligible for the proposed study. Based on our prior experience with similar patient population, we anticipate enrollment of 1 patient per month.

The planned sample size is 18 evaluable patients for dose expansion cohort. Conservatively allowing for up to 10% dropout, we will enroll up to 27 patients for an evaluable 18. Thus the maximal study period will be 54 months (30 months accrual plus 12 months study treatment plus 12 months survival follow-up). It is assumed that is sufficient to observe the minimum number completed cycles and to assess the time-to-event variables, including recurrence free survival and OS.

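### Protocol 6.7 replaces every patient who stops early, which conflicts with 8.2.1 and SAP 5.c; because the completion denominator is unsettled, treatment failures can drop out of the completion rates

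*Protocol*

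**What the plan says.** **Replacement.** Protocol 6.7 gives the reasons for permanently stopping both drugs. They include "Intolerable toxicity related to study treatment, including development of an immune mediated adverse event" and "Patients have Cystoscopy or Radiographic disease progression or symptomatic deterioration attributed to disease progression". The section ends: "Patients who discontinue study treatment prematurely will be replaced". It sets no limit on reason, grade or timing.

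Protocol 8.2.1, repeated almost word for word in SAP 5.c, has three narrower rules:
- Patients who stop because of toxicity from previous therapy are replaced for efficacy.
- "Patients removed from study for early withdraw or hypersensitivity reactions will be replaced if they have received less than 5 doses of study treatment". The dose count refers to the induction phase, and this sentence has no exception for grade or relatedness.
- Patients short of five induction doses "will be replaced unless the missed doses were due to development of grade 3-4 adverse events related to study treatment".

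Protocol 5.2.1.1 defines who is DLT-evaluable: a minimum number of doses and the full 42 days, "unless the patient discontinued the study treatment due to a DLT". It does not mention replacement.

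**Denominator.** Protocol 10.2 analyses patients evaluable under 8.1.1, meaning at least one dose of BCG and avelumab. SAP 5.a uses a similar population for compliance and safety. However, the note in Protocol 4.2 says evaluable patients are those of 8.2.1, and Protocol 10.3 sets recruitment in the same term: "we will enroll up to 27 patients for an evaluable 18". SAP 8.a reports the induction completion rate within Section 8, and SAP 5.c assigns that section's antitumor measures to the evaluable population (five or more doses plus a first assessment). The SAP names no population specifically for the Month 6 maintenance completion rate.

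**The concern.** Completion is what this trial measures. Protocol 1.2 and 6.4 call a patient who cannot complete induction a treatment failure, and the Month 6 endpoint in 2.2.2 counts unacceptable toxicity and progression as non-completion. Those events are also listed in 6.7 as reasons to stop, and 6.7 then calls for a substitute patient. A replacement rule that acts on the endpoint's own failures is harmless only if the replaced patients stay in the denominator.

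Two things are at stake. First, staff deciding during accrual whether to enrol a substitute have rules that give opposite answers for the same patient. Second, an analyst who takes the 18 evaluable patients as the denominator, or who follows the SAP's assignment of Section 8, can report a completion rate from which some failures have been removed.

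**Working it through.** **1. The rules applied to the same patients**

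| Patient | Protocol 6.7 | Protocol 8.2.1 / SAP 5.c |
|---|---|---|
| Stops both drugs in induction, fewer than 5 doses, related grade 3-4 event | Replaced | Not replaced |
| Removed from study, fewer than 5 doses, related grade 3-4 hypersensitivity | Replaced | Replaced by one sentence, not replaced by the next |
| Stops at Month 4 for a related immune event, after 5 doses and first assessment | Replaced | No rule |
| Taken off at Month 6 for high-grade disease | Replaced | No rule |

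The first row is a direct contradiction. The second is a conflict inside 8.2.1 itself.

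**2. The plan's own figure.** Protocol 10.1 gives n = 18, an expected Month 6 completion rate of 60%, and a two-sided 95% Wilson lower bound of 37.6%. The Wilson limits are

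[p + z²/2n ± z√(p(1−p)/n + z²/4n²)] / (1 + z²/n).

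With z = 1.96, p = 0.60 and n = 18: (0.6 + 0.1067 ± 0.2502)/1.2134, giving 37.6% to 78.9%. The stated bound reproduces. It corresponds to 10.8 completers; the nearest whole count, 11/18 = 61.1%, gives 38.6% to 79.7%.

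**3. Limiting cases at a true rate of 60%**
- No replacement, failures counted: about 11/18, CI 38.6% to 79.7%.
- Every failure replaced and dropped from the denominator: 18/18, CI 82.4% to 100%, whatever the true rate.
- Every non-completer replaced but all treated patients kept: 18/0.6 = 30 treated, and 18/30 = 60%, CI 42.3% to 75.4%. The rate is unbiased, but 30 exceeds the cap of 27.

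**4. Between the limits.** If a share r of failures is replaced and dropped, the expected rate is p/[p + (1−p)(1−r)]. The values of r, and the 80% row, are assumptions.

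| True rate p | r = 0 | 25% | 50% | 75% | 100% |
|---|---|---|---|---|---|
| 60% | 60% | 66.7% | 75% | 85.7% | 100% |
| 80% | 80% | 84.2% | 88.9% | 94.1% | 100% |

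**5. Enrolment if every non-completer is replaced.** The expected number treated is 18/p, and the chance that 27 patients yield at least 18 completers is a binomial tail. Rates other than 60% are assumptions.

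| True rate | Expected treated | P(at least 18 of 27) |
|---|---|---|
| 60% | 30 | 31% |
| 70% | 25.7 | 73% |
| 80% | 22.5 | 97% |
| 90% | 20 | >99.9% |

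If six of the 27 had been used at a failed dose level 1, P(at least 18 of 21) at 60% is 1.1%. The plan's 10% dropout allowance gives 18/0.9 = 20, or 26 with six such lead-in patients. The cap is therefore consistent with replacing dropouts but not with replacing a 40% failure share.

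**The case against.** The strongest reply is that replacement is not exclusion. No passage removes a replaced patient from the completion rates. Protocol 10.2 with 8.1.1, and SAP 5.a, keep anyone with at least one dose; 8.2.1 keeps early withdrawals in the safety analysis; and 6.9 follows patients who stop early. This stands. A reader might infer that 6.7 by itself deletes the failures and fixes the Month 6 rate at 100%. The documents do not support that: the 100% needs a denominator that 10.2 does not use. The reply does not settle the matter, because Protocol 4.2 and 10.3 and SAP 8.a with 5.c point to the other denominator. For induction completion, the SAP's five-dose condition is a cause in its own right, separate from 6.7.

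A reader might also infer that 6.7 contradicts 5.2.1.1 and undoes the 3+3 count. It does not. Section 5.2.1.1 defines evaluability and has no replacement rule; a patient who stops for a DLT stays counted whether or not someone else is enrolled. A clarifying sentence is worthwhile, but there is no textual contradiction.

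The 30 patients, 31% and 1.1% should not be read as forecasts. Section 6.7 concerns stopping both drugs permanently, and 6.4 allows one to continue while the other is held. A patient who misses the Month 6 criterion through delays but stays on treatment is a non-completer and is not replaced.

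The hypersensitivity overlap is also limited. Table 3 permanently discontinues avelumab after a grade 3-4 infusion reaction, which is not automatically removal from study. The two sentences collide only for patients actually removed.

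Finally, there is no hypothesis test and the sample size rests on feasibility, so a denominator above 18 would do no harm to the analysis.

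**Conclusion.** The conflict between Protocol 6.7 and Protocol 8.2.1 with SAP 5.c is explicit and needs no assumption. So is the overlap between the hypersensitivity sentence and the related grade 3-4 exception, for patients removed from study with fewer than five doses.

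The effect on the completion rates is a risk, not a certainty. It arises only if replaced patients leave the denominator, which some passages permit and others rule out. Its upper limit is 18/18 against about 11/18 at the plan's 60%. If half the failures were replaced and dropped, the expected rate would be 75%. The enrolment figure of 30 against a cap of 27 is likewise an upper bound, since it treats every Month 6 non-completer as a permanent discontinuation. No type I error or power statement is affected. The point still matters because completion is the primary endpoint, the trial is small and single-arm, and replacement decisions are taken while patients are accruing.

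**What to change.** 1. Delete the last sentence of Protocol 6.7 and refer instead to a single replacement rule in 8.2.1, mirrored in SAP 5.c.
2. In 8.2.1 and SAP 5.c, reconcile the hypersensitivity sentence with the exception for related grade 3-4 events, so that one patient cannot meet both.
3. State that any patient with at least one dose of each drug who stops for related toxicity or disease stays in the denominator of both completion rates as a non-completer, whether or not another patient is enrolled. Add that a DLT in the lead-in stays in the DLT count.
4. Name the at-least-one-dose population as the denominator for SAP 8.a and for the Month 6 completion rate. Align the note in Protocol 4.2 with this, so that evaluable has one stated meaning for each analysis.

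The cost is a wording amendment to the protocol and SAP. It adds no patients and calls for fewer replacements than 6.7 read literally. The reported completion rates may be slightly less favourable.

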6.8 Prohibited Medications

Patients are prohibited from receiving the following therapies during the screening and treatment phase of this study:

- Antineoplastic systemic chemotherapy or biological therapy
- Immunotherapy not specified in this protocol
- Chemotherapy not specified in this protocol
- Investigational agents other than avelumab and intravesical-BCG
- Systemic glucocorticoids for any purpose other than to modulate symptoms from a suspected immunologic etiology. The use of physiologic doses of corticosteroids may be approved after consultation with the Sponsor. In such cases, systemic steroids should be stopped at least 24 hours prior to the next dose of avelumab.
- **Note:** Inhaled steroids are allowed for the management of asthma.
- Live vaccines within 14 days prior to the first dose of study treatment and while participating in the study. Examples of live vaccines include, but are not limited to, the following: measles, mumps, rubella, chicken pox, yellow fever, and rabies and typhoid (oral) vaccine. Seasonal influenza vaccines for injection are generally killed virus vaccines and are allowed. Intranasal influenza vaccines (eg, Flu-Mist®) are live attenuated vaccines, however, and are not allowed.
- Prophylactic cytokines (G-CSF) should not be administered in the first cycle of the study but may be administered in subsequent cycles according to current ASCO guidelines [32].
- Any surgery that involves tumor lesions. Note: Administration of radiation therapy or surgery done that involves tumor lesions will be considered as disease progression at the time the procedure is performed.

If there is a clinical indication for any medication or vaccination specifically prohibited during the study, discontinuation from study therapy may be required. The Investigator should discuss any questions regarding this with the Sponsor. The final decision on any supportive therapy or vaccination rests with the Investigator and/or the patient's primary physician. The decision to continue the patient on study therapy, however, requires the mutual agreement of the Sponsor-Investigator and the patient.

6.9 Duration of Follow-up

The maximum follow-up period will be up to 1 year. For this protocol, all patients, including those who discontinue protocol therapy early, will be followed for response until progression or to the date of censoring (dropout, end of study), and for survival every three months. All patients must also be followed through completion of all protocol therapy. See Section 7.2.2 for additional details.

7 STUDY PARAMETERS

7.1 Therapeutic Parameters

- Screening procedures outlined on study calendar in Section 7.2. must be completed within 4 weeks prior to registration.
- Pre- study scans should be performed within 4 weeks prior to registration. Tumor assessment via CT or MRI will be optional at screening if data from standard care is available

- All patients must have a pre-dosing weight taken at every visit, as appropriate.
- All required pretreatment laboratory studies should be done as outlined in the study calendars in [Section 7.2](#).
- Initial H&P and laboratory tests can be used for C1D1 if done within 72 hours

7.2 Observations and Tests

The schedule of events to be performed during the study is provided in **Table 7**. All assessments must be performed and documented for each patient. Patients will be closely monitored for safety and tolerability throughout the study. Patients should be assessed for toxicity prior to each dose of avelumab and/or intravesical BCG; dosing will occur only if the clinical assessment and local laboratory test values are acceptable.

Table 7 Schedule of Events^l

Cycles	Screening	Induction Phase (cycle 1) ^a				Maintenance Phase				EOT	Follow-Up
						(Month 3, 6, 12)			Month 9		
Weeks		1-6		7-12		1-3		4-12		1-12	
Days	-28 to -1	1	22	43	64	1		22	Q4W	Q4W	
Informed Consent	X										
Eligibility review	X	X									
History & Physical	X	X ^b	X	X	X	X		X	X	X	
ECOG-PS	X	X ^b	X	X	X	X		X	X	X	X
Vital signs & weight	X	X	X	X	X	X		X	X	X	X
Toxicity assessment ^d	X	X ^d								X	
Con-meds	X	X	X	X	X	X		X	X	X	X
MRI / CT ^c	X	as clinically indicated									
CBC/Diff/ Plts ^d	X	X ^b	X	X	X	X		X	X	X	X
Serum chemistry ^e	X	X ^b	X	X	X	X		X	X	X	X
PT /PTT /INR	X	X ^b	If clinically indicated							X	

Cycles	Screening	Induction Phase (cycle 1) ^a				Maintenance Phase				EOT	Follow-Up
						(Month 3, 6, 12)					
Weeks		1-6		7-12		1-3		4-12		1-12	
Days	-28 to -1	1	22	43	64	1		22	Q4W	Q4W	
Urinalysis ^h	X	X ^b	X	X	X	X		X	X	X	X
TSH, FT3, and FT4	X	Repeat Q8W								X	
HIV, HBV, HCV serology	X										
Urine pregnancy test	X	X ^b	Repeat Q4W								
EKG ^f	X	If clinically indicated									
Blood sample for biomarkers ^g		X				X					
Urine sample for immunoassay ^h		X	X	X		X					
Avelumab IV dose ⁿ		X (Q1W)		X (Q2W)		X (Q1W)		X (Q2W)		X(Q2W)	
intravesical BCG		X (Q1W)				X (Q1W) C2, 3, 5					X
Cystoscopy ^m and urine cytology ⁱ	X					Repeat Q3M as SOC					
QOL ^j		X				X				X	
Survival											X ^k

a. Treatment cycles are 84 days (12 weeks) long, with visits on Day 1 of each BCG course, then every 4 weeks coinciding with Avelumab infusion, unless otherwise specified. All visits have a window of \pm 3 days (calculated in reference to Cycle 1/Day 1). The week following BCG therapy completion will not include avelumab treatment. Avelumab every two week therapy will start two weeks from the conclusion of BCG therapy and continue until the next BCG regimen. In the event

of an unforeseen event, such as a weather event, holiday, or center closure, the PI may alter treatment schedule by +/- 10 days to allow for resumption of therapy.

- b. If history, PE, ECOG-PS and screening laboratory tests are performed within 72 hours prior to first dose (Cycle 1, Day 1), repeat testing is not required.
- c. Tumor assessment via CT or MRI will be optional at screening if data from standard care is available.
- d. **Toxicity assessment is required prior to each BCG and/or avelumab treatment.** If dose interruption or modification is required at any point on study because of hematologic toxicity, weekly CBC will be monitored until the AE resolves, and to ensure safety of the new dose, weekly blood draws for CBC will be also required for an additional 4 weeks after the AE has been resolved to the specified levels, after which monitoring every 3 weeks may resume.
- e. Consisting of albumin, alkaline phosphatase, BUN, calcium, carbon dioxide (CO₂), chloride, creatinine, glucose, potassium, AST, ALT, sodium, total bilirubin, total protein
- f. Patients will undergo EKG monitoring at screening. Additional EKG at pre-dose on day 1 of each cycle and EOT if clinical indicated.
- g. Blood sample for exploratory biomarkers will be collected at pre-dose on day 1 of induction therapy; and at pre-dose on day 1 of month 3 and month 6 maintenance therapy.
- h. Urine sample will be collected at pre-dose on days 1, 22 and 43 of induction treatment; and at pre-dose on day 1 of Months 3 and 6 Maintenance for measurement by multiplexed immunoassay for immune response biomarkers.
- i. Cystoscopy and urine cytology will be obtained at screening and at Month 3, 6, 9, and 12 and at EOT. Only frankly malignant cytology will be considered positive and used to determine the need for bladder biopsy and further evaluation.
- j. Patient will be asked to complete EORTC QLQ-C30 to measure QOL on BCG [33].
- k. Every three months for up to one year. See Sections 7.2.1 and 7.2.2 for additional details.
- l. During the COVID-19 crisis, protocol mandated visits may be performed via telemedicine or visits may be combined in order to prevent imminent safety risks to patients. All such changes to the visit schedule must be clearly documented in the subject's chart. Changes in study visit schedules or missed visits must be explained in the final clinical study report.
- m. For the subset of patients with CIS (with or without concomitant Ta or T1 disease) at study entry, a 6-month biopsy is required. A negative biopsy at 6 months will provide evidence of complete response. A +/- 10 day window will be allowed around the disease assessment time point. Patients receiving a second induction will not be required to undergo 6-month biopsy.
- n. Following avelumab infusions, patients must be observed for 30 minutes post infusion for potential infusion related reactions.

